### 3 OBJECTIVES AND ENDPOINTS

**Table 1 - Objectives and endpoints**

Objectives	Endpoints
Primary  To demonstrate the superiority of once-weekly injection of efpeglenatide 2, 4, or 6 mg in comparison to placebo in HbA1c change from baseline to Week 30 in participants with T2DM inadequately controlled with diet and exercise	

Change from baseline to Week 30 in HbA1c

Secondary  To demonstrate the superiority of once-weekly injection of efpeglenatide 2, 4, and 6 mg in comparison to placebo on glycemic control  To demonstrate the superiority of once-weekly injection of efpeglenatide 2, 4, and 6 mg in comparison to placebo on body weight  To evaluate the safety of once-weekly injection of efpeglenatide 2, 4, and 6 mg	

Number of participants with HbA1c <7% at Week 30

Change from baseline to Week 30 in fasting plasma glucose (FPG)

Change from Baseline to Week 56 in HbA1c

Change from baseline to Weeks 30 and 56 in body weight

Number of participants with at least one hypoglycemic event during treatment period

Number of hypoglycemic events per participant-year during treatment period

Number of participants with AEs (see Section 8.3)

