Multiplicity considerations	
To control the family-wise type I error, a step-down testing procedure will be applied. For the primary efficacy endpoint (change from Baseline to Week 30 in HbA1c), the 3 efpeglenatide doses will be tested in the order of 6 mg, 4 mg, and 2 mg. once the primary endpoint is statistically significant at <math>\alpha=0.05</math> (2-sided) for all 3 efpeglenatide doses, a hierarchical testing procedure will be performed to test the following study secondary efficacy endpoints by the following prioritized order:
 
 
1. HbA1c <7% at Week 30 for efpeglenatide 6 mg versus placebo (yes/no)
 
2. HbA1c <7% at Week 30 for efpeglenatide 4 mg versus placebo (yes/no)
 
3. Change from Baseline to Week 30 in body weight (kg) for efpeglenatide 6 mg versus placebo
 
4. Change from Baseline to Week 30 in body weight (kg) for efpeglenatide 4 mg versus placebo
 
5. HbA1c <7% at Week 30 for efpeglenatide 2 mg versus placebo (yes/no)
 
6. Change from Baseline to Week 30 in FPG (mmol/L, mg/dL) for efpeglenatide 6 mg versus placebo
 
7. Change from Baseline to Week 30 in FPG (mmol/L, mg/dL) for efpeglenatide 4 mg versus placebo
 
8. Change from Baseline to Week 56 in body weight (kg) for efpeglenatide 6 mg versus placebo
 
9. Change from Baseline to Week 56 in HbA1c (%) for efpeglenatide 6 mg versus placebo
 
10. Change from Baseline to Week 56 in body weight (kg) for efpeglenatide 4 mg versus placebo
 
11. Change from Baseline to Week 56 in HbA1c (%) for efpeglenatide 4 mg versus placebo
 
12. Change from Baseline to Week 56 in HbA1c (%) for efpeglenatide 2 mg versus placebo
 
13. Change from Baseline to Week 56 in body weight (kg) for efpeglenatide 2 mg versus placebo
 
 
The testing will stop as soon as an endpoint for an efpeglenatide dose is found to be not statistically significant at <math>\alpha=0.05</math> (2-sided) for 1 efpeglenatide dose. No multiplicity adjustment will be made on other secondary efficacy variables or the comparison of other efpeglenatide dose versus placebo than mentioned above.

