1.2.2 Secondary objectives

Secondary objectives of this study include:

- To demonstrate the superiority of once-weekly injection of efpeglenatide 2, 4, and 6 mg in comparison to placebo on glycemic control parameters (number of participants who achieve HbA1c goal of <7.0%, HbA1c, fasting plasma glucose [FPG]);
- To demonstrate the superiority of once-weekly injection of efpeglenatide 2, 4, and 6 mg in comparison to placebo on body weight;
- To evaluate the safety of once-weekly injection of efpeglenatide 2, 4, and 6 mg.

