2.1.3.2 Secondary efficacy endpoints

- HbA1c < 7.0% at Week 30 (yes/no);
- Change in FPG from Baseline to Week 30;
- Change in HbA1c (%) from Baseline to Week 56;
- Changes in body weight from Baseline to Weeks 30 and 56.

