2.1.3.3 Exploratory efficacy endpoint(s)

- Patient qualitative assessment of treatment version 2 (PQAT v2) at Weeks 30 and 56;
- HbA1c < 7.0% at Week 56 (yes/no);
- Change in FPG from Baseline to Week 56;
- Changes in 7-point SMPG profiles (mmol/L, mg/dL: mean 24-hour SMPG) from Baseline to Weeks 30 and 56;
- Change in plasma glucose excursions (2-hours PPG minus preprandial plasma glucose at breakfast, lunch, and dinner) based on 7-point SMPG data from baseline to Week 30 and Week 56;
- Rescue therapy used during the treatment period until Weeks 30 and 56 (yes/no);
- Time to initiation of rescue therapy (weeks).

Mean 24-hour SMPG is the average over the available plasma glucose values from the 7 time points and can only be calculated if at least 4 points are available.

Prandial glucose excursions are calculated by subtracting the preprandial value from the postprandial value respectively for breakfast, lunch, and dinner.

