Treatment compliance will be summarized descriptively as quantitative variables (number, mean, SD, median, minimum, and maximum). The percentage of participants whose compliance is <60, ≥60 and <80, ≥80% and ≤100%, or >100% will be summarized.

Cases of overdose will constitute AESIs and will be listed as such.

2.4.3.3 *Frequency of injections*

The frequency of injections during the whole on-treatment period will be summarized separately by time of day (morning, afternoon, evening, night) and location of injection (Abdomen, Other, Missing). For analysis purposes, morning is defined as the time between 06:00-11:59, afternoon as between 12:00-17:59, evening as between 18:00-23:59, and night as between 00:00-05:59.

2.4.4 *Analyses of efficacy endpoints*

Efficacy analyses will be performed on the ITT population using efficacy assessment collected during the study, including those obtained after IMP discontinuation and/or introduction of rescue therapy, unless otherwise specified (see [Section 2.5.4](#)).

Due to COVID-19 pandemic, participants may not be able to maintain their regular clinical visits according to the study protocol, with the closure of facilities, safety concern for the participants to go to the sites, unavailability of the investigators for treating participants, interruption of transportation or other COVID-19 related reasons. Data missingness due to these reasons is likely to be missing at random. For a continuous endpoint, all observed data of participants within the

same treatment group can be used for imputation in an MAR approach. Sensitivity analyses will be performed to take into consideration of the impact of COVID-19 if the number of participants with missing endpoint data due to COVID-19 is above the threshold as specified in the following sections.

Of note, it is unlikely that the efficacy analyses at Week 30 in EFC14822 would be impacted by COVID-19 as the last Week 30 visit was performed on 29Jan2020. However, the efficacy analyses at Week 56 is likely to be impacted.

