2.4.4.2.1 HbA1c $<7.0\%$ at Week 30 (yes/no)

Proportions of participants achieving the HbA1c target value of $<7.0\%$ at Week 30 will be compared by treatment group using a Cochran-Mantel-Haenszel (CMH) test stratified by randomization stratum of Screening HbA1c ($<8.0, \geq 8.0\%$) and Visit 3 (Baseline, Day 1) BMI ($<30, \geq 30 \text{ kg/m}^2$) in the ITT population. All HbA1c values at Week 30 will be used to determine whether a participant is a responder (HbA1c $<7.0\%$) or not, even if they are measured after IMP discontinuation or introduction of rescue therapy. Participants with missing HbA1c data at Week 30 will be considered not achieving HbA1c $<7.0\%$. The nominal p-value from the CMH test will be presented. No rounding for HbA1c will be done.

2.4.4.2.2 Changes from baseline in FPG to Week 30 and in body weight to Weeks 30 and 56 and in HbA1c to Week 56

Changes from Baseline in FPG to Week 30, in body weight to Weeks 30 and 56 and in HbA1c to Week 56 will each be analyzed by the same ANCOVA model with missing values imputed by MI method as described in [Section 2.4.4.1](#) the primary analysis. The least squares (LS) means, standard errors of LS means within each treatment group and the adjusted mean and associated two-sided 95% CI of the difference between efpeglenatide 2, 4, and 6 mg and placebo group will be presented.

Summary statistics at protocol scheduled visits and for the last on-treatment value will also be provided for FPG and body weight.

Additional Analysis

Analysis on completers at Week 30 (body weight)

For participants in ITT population who completed the 30-week core treatment period and did not start any rescue therapy before the end of the period, the secondary endpoint of change from Baseline in body weight to Weeks 30, will be assessed too by the same ANCOVA model as used for the primary analysis using the observed values.

Analysis on completers at Week 56 (HbA1c and body weight)

For participants in ITT population who completed the whole on-treatment period and did not start any rescue therapy before the end of the period, the change from Baseline in HbA1c and body weight to Weeks 56, will be assessed by the same ANCOVA model as used for the primary analysis using the observed values.

Sensitivity analysis due to COVID-19 at Week 56 (HbA1c and body weight)

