2.4.4.3 Multiplicity issues

To protect the family-wise error rate for the secondary endpoint, the adjustment for multiplicity of comparison will be applied.

For secondary endpoints, a step-down testing procedure will be applied. For the primary efficacy endpoint (change from Baseline to Week 30 in HbA1c), the 3 efpeglenatide doses will be tested in the order of 6 mg, 4 mg, and 2 mg. Once the primary endpoint is statistically significant at $\alpha=0.05$ (2-sided) for all 3 efpeglenatide doses, a hierarchical testing procedure will be performed to test the following study secondary efficacy endpoints by the following prioritized order:

1. HbA1c $<7\%$ at Week 30 for efpeglenatide 6 mg versus placebo (yes/no)
2. HbA1c $<7\%$ at Week 30 for efpeglenatide 4 mg versus placebo (yes/no)
3. Change from Baseline to Week 30 in body weight (kg) for efpeglenatide 6 mg versus placebo

4. Change from Baseline to Week 30 in body weight (kg) for efpeglenatide 4 mg versus placebo
5. HbA1c <7% at Week 30 for efpeglenatide 2 mg versus placebo (yes/no)
6. Change from Baseline to Week 30 in FPG (mmol/L, mg/dL) for efpeglenatide 6 mg versus placebo
7. Change from Baseline to Week 30 in FPG (mmol/L, mg/dL) for efpeglenatide 4 mg versus placebo
8. Change from Baseline to Week 56 in body weight (kg) for efpeglenatide 6 mg versus placebo
9. Change from Baseline to Week 56 in HbA1c (%) for efpeglenatide 6 mg versus placebo
10. Change from Baseline to Week 56 in body weight (kg) for efpeglenatide 4 mg versus placebo
11. Change from Baseline to Week 56 in HbA1c (%) for efpeglenatide 4 mg versus placebo
12. Change from Baseline to Week 56 in HbA1c (%) for efpeglenatide 2 mg versus placebo
13. Change from Baseline to Week 56 in body weight (kg) for efpeglenatide 2 mg versus placebo

Based on the hierarchical testing above, the testing will stop as soon as an endpoint for an efpeglenatide dose is found to be not statistically significant at $\alpha=0.05$ (2-sided). No multiplicity adjustment will be made on other secondary efficacy variables or the comparison of other efpeglenatide dose versus placebo than mentioned above.

2.4.4.4 *Exploratory efficacy analysis*

2.4.4.4.1 *HbA1c <7.0 % at Week 56 (yes/no)*

Proportions of participants achieving HbA1c target values of <7.0% at Week 56 will be analyzed by same approach described in secondary endpoint: HbA1c < 7% at Week 30.

2.4.4.4.2 *Change in FPG from baseline to Week 56*

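### The secondary hierarchy gives efpeglenatide 2 mg no error-controlled test on FPG at any visit, and one on body weight only at Week 56; two steps added at the end would close both gaps without affecting the existing tests

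*SAP*

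**What the plan says.** The SAP's secondary objectives (1.2.2) are to show superiority of 2, 4 and 6 mg over placebo "on glycemic control parameters (number of participants who achieve HbA1c goal of <7.0%, HbA1c, fasting plasma glucose [FPG"]) and on body weight. Protocol Table 1 has the same three-dose wording for weight: "To demonstrate the superiority of once-weekly injection of efpeglenatide 2, 4, and 6 mg in comparison to placebo on body weight". Its glycemic objective refers to glycemic control without naming FPG, but lists Week 30 FPG as a secondary endpoint.

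SAP 2.1.3.2 lists five secondary efficacy endpoints: HbA1c below 7% at Week 30, "Change in FPG from Baseline to Week 30", HbA1c change to Week 56, and body weight change to Weeks 30 and 56. FPG at Week 56 ("Change in FPG from Baseline to Week 56") is exploratory under SAP 2.1.3.3.

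SAP 2.4.4.3 and protocol Table 5 give the same procedure. The primary endpoint is tested for 6, 4 and then 2 mg. If all three succeed, 13 secondary comparisons follow in fixed order, each at two-sided 0.05, stopping at the first failure. The 2 mg dose appears at step 5 (HbA1c below 7%, Week 30), step 12 (HbA1c, Week 56) and step 13 ("Change from Baseline to Week 56 in body weight (kg) for efpeglenatide 2 mg versus placebo"). For everything else, "No multiplicity adjustment will be made on other secondary efficacy variables or the comparison of other efpeglenatide dose versus placebo than mentioned above". The unlisted comparisons are still estimated: under SAP 2.4.4.2.2, for each continuous secondary endpoint, the "two-sided 95% CI of the difference between efpeglenatide 2, 4, and 6 mg and placebo group will be presented".

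**The concern.** The objectives name three doses, and FPG and body weight are among the parameters to be shown superior. At 2 mg, FPG has no place in the controlled sequence at Week 30, and Week 56 FPG is exploratory. Body weight at 2 mg is confirmatory at Week 56 but not at Week 30, and neither document gives a reason for the difference.

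What is at stake is what the trial may conclude. Even if all 3 primary and all 13 secondary tests succeed, the plan permits no error-controlled statement that 2 mg lowers FPG, or that it reduces weight by Week 30. If those two results were instead read at a nominal 0.05 each, the chance of at least one false positive when both effects are null would be 1 - 0.95² = 0.0975 for independent tests (0.097 with an assumed correlation of 0.2).

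**Working it through.** **1. The plan's own power figure.** Inputs from SAP 1.3: 100 per arm, SD 1.1%, two-sided 0.05. The standardized effect is δ / (1.1 × √(2/100)) = δ / 0.1556.
- δ = 0.5: 3.214, power Φ(3.214 - 1.960) = 0.895 (0.892 with the t distribution). Stated: 89%.
- δ = 0.6: 3.857, power Φ(3.857 - 1.960) = 0.971 (0.970 with t). Stated: 96%.

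Both agree to within about a percentage point.

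**2. Coverage of the hierarchy.** Five secondary endpoints by three doses make 15 pairs. That count is mine; the documents define no 15-test family.

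| Endpoint | Doses in the hierarchy (steps) |
|---|---|
| HbA1c <7%, Week 30 | 6, 4, 2 mg (1, 2, 5) |
| Body weight, Week 30 | 6, 4 mg (3, 4) |
| FPG, Week 30 | 6, 4 mg (6, 7) |
| Body weight, Week 56 | 6, 4, 2 mg (8, 10, 13) |
| HbA1c, Week 56 | 6, 4, 2 mg (9, 11, 12) |

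3 + 2 + 2 + 3 + 3 = 13. The two missing are 2 mg Week 30 body weight and 2 mg Week 30 FPG.

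**3. Error rate with two steps added.** In a fixed sequence, a false rejection requires rejecting the first true null in the order, which has probability at most 0.05. This holds for any correlation and for either order of the added steps. Simulation of the 18-test chain (400,000 runs, shared placebo arm) gave family-wise error of 0.0495 to 0.0506 across null configurations, with Monte Carlo error about 0.0003. Rejection rates for the 16 existing tests were identical with and without the added steps, as they must be.

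**4. Chance of obtaining the new claims.** The documents give no power, effect size or SD for any secondary endpoint, so these figures rest on assumptions. Primary tests have the standardized means of item 1. Correlation between two tests is the between-endpoint value r (assumed 0.3 or 0.6), multiplied by 0.5 when the doses differ, because placebo is shared. FPG is placed at step 14. All three primary tests succeed with probability 0.93 at -0.6% and 0.77 at -0.5%.

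| Assumed power of secondary tests (primaries at -0.6%) | 2 mg FPG claim (step 14), r = 0.3 to 0.6 | Both new claims (through step 15) |
|---|---|---|
| 95% at all doses | 0.59–0.68 | 0.58–0.67 |
| 90% at all doses | 0.40–0.51 | 0.38–0.50 |
| 80% at all doses | 0.18–0.30 | 0.17–0.29 |
| 95% at 4 and 6 mg, 70% at 2 mg | 0.28–0.39 | 0.24–0.36 |
| 95% at 4 and 6 mg, 50% at 2 mg | 0.12–0.22 | 0.09–0.19 |

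With primaries at -0.5%, the step 14 figures for the first three rows are 0.52–0.61, 0.36–0.48 and 0.17–0.29. Lower correlation reduces them: at 90% power, -0.6% and r = 0, step 14 is passed with probability 0.29. Under the present plan the corresponding probability is 0 whatever the data.

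**The case against.** The strongest reply is that nothing is wrong. The chain controls type I error, and both documents state openly that unlisted comparisons are unadjusted. The protocol's amendment summary shows that the order was deliberately reworked, with 2 mg Week 56 body weight added. The body-weight objective names no visit, and 2 mg weight is tested at step 13. Glycemic control at 2 mg has the primary test and steps 5 and 12. FPG is named only in the SAP's version of the objective, and its 2 mg effect is still reported with a 95% CI. All of this stands, and it is why the point is only an improvement.

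A reader might infer that the omission inflates error, or that the plan contradicts its objectives by failing to test every dose on every endpoint. The documents support neither. The unlisted pairs are outside the claimed family, and no passage promises a controlled test for each dose, endpoint and visit.

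A second objection is that equal power at all doses flatters the gain, since protocol 4.3 reports efficacy rising up to the highest dose tested. That is fair, and the last two table rows show the effect.

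A third is timing. SAP 2.4.4 records that "the last Week 30 visit was performed on 29Jan2020", and 29 January + 182 days = 29 July 2020 suggests that Week 56 visits were also largely complete before SAP version 3 (19 August 2020). Protocol 6.3.1 masks HbA1c and FPG from investigators but does not mention body weight. SAP version 3 did change a Week 30 analysis, but removing a sensitivity analysis is not comparable to adding confirmatory claims. A blinded addition can still be valid, but the blinding must be documented.

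**Conclusion.** The point holds as a limited improvement to a valid hierarchy. The 2 mg dose has no error-controlled FPG test at any visit and a controlled body-weight test only at Week 56. Two last steps would open both claims at no cost in alpha or power to the 3 primary and 13 secondary tests.

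The benefit is conditional: both added steps are reached only if all 16 earlier tests succeed, including the Week 56 tests at steps 8 to 13. On the assumptions tabulated, with primaries at -0.6%, the chance of the 2 mg FPG claim ranges from about 0.12 to 0.68. Where it falls depends mainly on 2 mg secondary power, which the documents do not give. The coverage count and the error-rate result do not depend on those assumptions.

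**What to change.** Before database lock and unblinding, add to SAP 2.4.4.3:
- Step 14: change from Baseline to Week 30 in FPG, efpeglenatide 2 mg versus placebo.
- Step 15: change from Baseline to Week 30 in body weight, efpeglenatide 2 mg versus placebo.

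Each is tested at two-sided 0.05 only if every earlier step succeeds. FPG goes first because it has no other controlled route; weight already has step 13.

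Record the change in SAP Table 2 (section 1.6) with its date and a statement that it was made blind to treatment assignment and results. Align protocol Table 5, or document the deviation from it, so that the two confirmatory lists do not silently differ.

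No new analysis is needed, because both ANCOVAs are already planned in SAP 2.4.4.2.2. The cost is the document change and the blinding record. Protocol 9.4 allows the SAP to be finalized up to database lock, and protocol 6.3.2 withholds the randomization code from the clinical team until then. The documents do not give the actual lock date; if unblinding has occurred, the change is no longer available and the two comparisons should be reported as unadjusted estimates.

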2.4.5 Analyses of safety data

The summary of safety results will be presented by treatment group on the “30-week core on-treatment period” and on the “whole on-treatment period” as defined in [Section 2.1.4](#). Selected tables will be displayed by treatment group on the “30-week on study observation period” as defined in [Section 2.1.4](#).

General common rules

All safety analyses will be performed on the safety population as defined in [Section 2.3.2](#), unless otherwise specified, using the common rules noted below. Safety data in participants who do not belong to the safety population (eg, treated but not randomized) will be listed separately.

- The Baseline value is defined in [Section 2.1.1](#). For WBC and differential counts, the baseline is defined as the last available value before the first injection of IMP where no differential component is missing.
- Last on-treatment value is defined as the value collected at or just prior to the last IMP intake.

- The potentially clinically significant abnormality (PCSA) values are defined as abnormal values considered medically important by the Sponsor according to predefined criteria/thresholds based on literature review and defined by the Sponsor for clinical laboratory tests, vital signs, and ECG (PCSA version 3 date dated 21 May 2014 effective date 24 May 2014 [[Appendix B](#)]).
 - PCSA criteria will determine which participants had at least 1 PCSA during the 30-week core on-treatment period and whole on-treatment period, taking into account all evaluations performed during the 30-week core on-treatment period and whole on-treatment period, including nonscheduled or repeated evaluations. The number of all such participants will be the numerator for the 30-week core on-treatment period and whole on-treatment period PCSA percentage.
 - The treatment-emergent PCSA denominator by group for a given parameter will be based on the number of participants assessed for that given parameter in the 30-week core on-treatment period and whole on-treatment period by treatment group on the safety population.
- For quantitative safety parameters based on central laboratory/reading measurements, descriptive statistics will be used to summarize results and change from Baseline values by visit and treatment group.
- The analysis of the safety variables will be, essentially, descriptive and no systematic testing is planned. Relative risks versus placebo and their 95% CIs may be provided, if relevant.
- Selected safety analyses will be summarized by age group, gender, racial subgroups, and any pertinent subgroups as appropriate.

2.4.5.1 Analyses of adverse events

Generalities

The primary focus of AE reporting will be on TEAEs. Pretreatment and posttreatment AEs will be described separately.

If an AE date/time of onset (occurrence, worsening, or becoming serious) is incomplete, an imputation algorithm will be used to classify the AE as pretreatment, treatment-emergent, or posttreatment. The algorithm for imputing date/time of onset will be conservative and will classify an AE as treatment emergent unless there is definitive information to determine it is pretreatment or posttreatment. Details on classification of AEs with missing or partial onset dates are provided in [Section 2.5.3](#).

Incidence tables will present AEs by SOC, HLT, HLT, and PT, sorted in SOC internationally agreed order and HLT, HLT and PT sorted alphabetically for each treatment group, and the number (n) and percentage (%) of participants experiencing an AE. Multiple occurrences of the same event in the same participant will be counted only once in the tables within a treatment phase. The denominator for computation of percentages is the safety population within each treatment group.

Sorting within tables ensures the same presentation for the set of all AEs within the observation period (pretreatment, treatment-emergent, and posttreatment). For that purpose, the table of all TEAEs presented by primary SOC and PT sorted by the internationally agreed SOC order and decreasing frequency of PTs within SOCs will define the presentation order for all other tables unless otherwise specified. In case of equal frequencies of PTs within a SOC, the alphabetic order will be applied. Sorting will be based on the incidence in the efpeglenatide 6 mg group.

The internationally agreed order of SOCs shown below was described in the Introductory Guide MedDRA Version 19.1, September 2016 International Conference on Harmonisation for SOC:

1. Infections and infestations
2. Neoplasms benign and malignant (including cysts and polyps)
3. Blood and lymphatic system disorders
4. Immune system disorders
5. Endocrine disorders
6. Metabolism and nutrition disorders
7. Psychiatric disorders
8. Nervous system disorders
9. Eye disorders
10. Ear and labyrinth disorders
11. Cardiac disorders
12. Vascular disorders
13. Respiratory, thoracic, and mediastinal disorders
14. Gastrointestinal disorders
15. Hepato-biliary disorders
16. Skin and subcutaneous tissue disorders
17. Musculoskeletal, connective tissue, and bone disorders
18. Renal and urinary disorders
19. Pregnancy, puerperium, and perinatal conditions
20. Reproductive system and breast disorders
21. Congenital and familial/genetic disorders
22. General disorders and administration site conditions
23. Investigations
24. Injury, poisoning, and procedural complications
25. Surgical and medical procedures
26. Social circumstances
27. Product issues

Analysis of all treatment-emergent adverse events

The following TEAE summaries will be generated for the safety population.

- Overview of TEAEs, summarizing number (%) of participants with any
 - TEAE
 - Serious TEAE
 - TEAE leading to death
 - TEAE leading to permanent treatment discontinuation
 - Treatment-related TEAE
 - TEAEs of special interest (AESI)
 - TEAEs requiring specific monitoring (AERSM)
- All TEAEs by primary SOC, HLGT, HLT, and PT, showing number (%) of participants with at least 1 TEAE sorted by the SOC internationally agreed order. The other levels (HLGT, HLT, PT) will be presented in alphabetical order. This sorting order will be applied to all other tables by SOC, HLGT, HLT, and PT, unless otherwise specified.
- All TEAEs by primary SOC and PT, showing the number (%) of participants with at least 1 TEAE, sorted by the internationally agreed SOC order and by decreasing incidence of PTs within each SOC. This sorting order will be applied to all other tables by SOC and PT, unless otherwise specified.
- All TEAEs related to IMP by primary SOC, HLGT, HLT and PT, showing the number (%) of participants with at least 1 TEAE
- All TEAEs by maximal intensity, presented by primary SOC and PT, showing the number (%) of participants with at least 1 TEAE by intensity (ie, mild, moderate, or severe)
- Summary of common TEAEs (eg, PTs with incidence $\geq 2\%$ in any treatment group) will also be presented by primary SOC, and PT
- Summaries of common TEAEs (eg, PTs with an incidence $\geq 2\%$ in any treatment group) will be provided as appropriate by primary SOC and PT and by demographic factors including gender (Male, Female), age group (<50 , ≥ 50 to <65 , ≥ 65 to <75 , ≥ 75 years), and race (Asian, Black or African American, White, Other)

Note: For all efficacy and safety subgroup analyses, race groups “Not reported”, “Unknown”, and participants who report more than one race will be considered “Other”.

- Kaplan-Meier curves will be provided for the time to first onset of the following PTs: nausea, vomiting, and diarrhea
- The frequency of TEAEs over time will be provided for nausea, vomiting, and diarrhea, using weekly time intervals through Week 8 and then every 4 weeks through Week 56, ie, [0-1] week, [1-2] weeks, [2-3] weeks, [3-4] weeks, etc. In each time interval, the numerator in the calculation of percentages will be the number of participants with at least 1 TEAE occurring in this time interval. Two types of analyses will be included: (1) only

the first event will be counted for each participant and all recurrent events will not be included, and the denominator for the calculation of percentages will be the number of participants at risk at the beginning of the time interval who did not experience a first event in the preceding intervals; and (2) the recurrent events in subsequent intervals will be counted once for each participant in the numerator of the corresponding interval, and the denominator for the calculation of percentages will be the number of participants at risk at the beginning of the time interval. A histogram of the frequency over time (by weekly intervals) will also be presented as appropriate.

- All TEAEs by BMI subgroup (< 30, \geq 30 kg/m²)
- All TEAEs by Anti-Efpeglenatide Antibody Status (Positive, Negative)

Analysis of all treatment emergent serious adverse event(s)

- All serious TEAEs by primary SOC, HLGT, HLT, and PT, showing the number (%) of participants with at least 1 serious TEAE

All serious TEAEs related to IMP, by primary SOC and PT, showing the number (%) of participants with at least 1 serious TEAE.

Analysis of all treatment-emergent adverse event(s) leading to treatment discontinuation

All TEAEs leading to treatment discontinuation, by primary SOC, HLGT, HLT, and PT, showing the number (%) of participants

Analysis of adverse events of special interest and adverse events requiring specific monitoring

Adverse events of special interest (AESI) and adverse events requiring specific monitoring (AERSM) include AE defined in [Section 2.1.4](#) and the criteria of AESI and AERSM are in [Table 3](#).

Table 3 - Criteria for AESI and AERSM

AE Grouping	Criteria
AESI	
Pregnancy	“Pregnancy” or “Partner pregnancy” checked
Symptomatic Overdose	“Overdose” checked and symptomatic (AEOVSYMP) = “Yes”
Increase in ALT >3 ULN	“ALT Increase” checked and Yes to the question “Is the event an AESI?” in eCRF form “Adverse Events”
AERSM	
Severe GI event	AE severity = “severe” using Gastrointestinal disorders CMQ
Severe hypoglycemia	Any hypoglycemia event which required assistance (from hypoglycemia page)
Pancreatic event	Cases reported in eCRF “Suspected or confirmed Pancreatitis” page or AE Category = “Pancreatic Neoplasm”

AE Grouping	Criteria
Selected cardiovascular event	Cases reported in the following specific eCRF pages: 
• "Suspected or confirmed MI/Unstable Angina"• "Suspected or confirmed cerebrovascular event"• "Suspected or confirmed heart failure" led to unplanned hospitalization, led to urgent/unscheduled visit to emergency room or an urgent/unscheduled outpatient heart failure treatment unit, or infusion center, or office/practice visit, not followed by hospitalization, or occurred while patient was hospitalized for another reason• Primary cause of death in eCRF "Death (CV)" as Acute MI, Sudden cardiac death, Heart failure or cardiogenic shock, Stroke, Complication of cardiovascular procedure, Other cardiovascular cause, or Undetermined cause of death
Calcitonin and thyroid C-cell neoplasm	Using Calcitonin increase CMQ
Acute renal failure	Using Acute renal failure CMQ
Severe injection site reaction	Intensity = "Severe" + Using Injection site reaction_ CMQ.
Severe allergic reaction	Intensity = "Severe" + CMQs for anaphylactic reaction, angioedema, severe cutaneous adverse reaction, anaphylactic/anaphylactoid shock conditions (under SMQ "Shock"), and hypersensitivity.
Severe immune complex disease	Intensity = "Severe" using Immune complex disease CMQ
Diabetic retinopathy complications	Cases reported in eCRF "Diabetic Retinopathy Complementary Form"

The following TEAE summaries will be generated for the safety population:

- All AESI by prespecified grouping and PT, showing number (%) of participants with at least 1 AESI, with PTs sorted by decreasing order in Efpeglenatide 6 mg group.
- All AERSM by prespecified grouping and PT, showing number (%) of participants with at least 1 AERSM, with PTs sorted by decreasing order in Efpeglenatide 6 mg group.

Separate AESI listings will be provided for pregnancy, overdose, and ALT increase, as well as an overall listing for AERSM.

Analysis of adjudicated events

All events of death, selected cardiovascular events (MI, stroke, unstable angina leading to hospitalization, and heart failure leading to hospitalization), any pancreas-related events, and other selected AEs (as defined in the CEC charter) will be reviewed, assessed and adjudicated by CEC.

The number of events confirmed by adjudication, will be summarized by treatment group.

Analysis of pretreatment and posttreatment adverse events

- All pretreatment AEs by primary SOC and PT, showing the number (%) of participants with at least 1 pretreatment AE
- All posttreatment AEs by primary SOC and PT, showing the number (%) of participants with at least 1 posttreatment AE
- All pretreatment SAEs by primary SOC and PT, showing the number (%) of participants with at least 1 pretreatment SAE
- All posttreatment SAEs by primary SOC and PT, showing the number (%) of participants with at least 1 posttreatment SAE.

Analysis of adverse events during the 30-week on study observation period

The following selected AE will also be summarized for the 30-week on-study observation period as defined in [Section 2.1.4](#):

- Overview of AEs
- AEs (by primary SOC, HLGT, HLT, and PT, showing number (%) of participants with at least 1 adverse event)
- SAE (by primary SOC, HLGT, HLT, and PT, showing number (%) of participants with at least 1 serious adverse event)
- AEs leading to death.

Analysis of COVID-19 related adverse events

COVID-19 related AEs during the whole on-treatment period will be presented for the number (%) of participants with at least one event and by primary SOC and PT.

Listings

Supportive AE listings will be provided for all SAEs, AESIs/AERSM, AEs leading to death, and AEs leading to treatment discontinuation. These listings will include at least the following information, sorted by treatment, participant identification, and onset date: treatment, participant identification, country, age, gender, race, primary SOC, PT, reported term, onset date, study day (relative day to the start date of IMP), AE duration, duration of exposure, intensity, corrective treatment, action taken with IMP, relationship to IMP/NIMP/study procedures, outcome, date of death (if any), seriousness, seriousness criteria, and AE status (“Pre” for a pre-treatment AE; “T” for a TEAE; and “Post” for a post-treatment AE).

Similar to the AE listing, a listing for all adjudicated AEs will be provided with adjudication outcome.

